4.1.1 General Design Description

We will conduct a phase 1 clinical trial with two groups randomly assigned in parallel. The experimental group (PD-MI) will receive mental imagery training and the control group (PD-Con) will receive psychoeducation (see Figure 3).

Within two weeks of obtaining consent and completing initial phone and online video-screening, subjects will complete online surveys and arrive for an in-person visit to complete the screening process including the comprehensive evaluation of baseline cognitive functioning, performance-based tests, and neurological exam. At the end of this visit, eligible subjects will be randomized to two groups, PD-MI and PD-Con.

Within two weeks of Visit 1, subjects will return for Visit 2 to assess baseline imagery skills and perform fMRI tasks in the scanner. Subjects in the PD-MI group will be interviewed in Visit 2 to gather information about their daily activities and goals for imagery script development.

Following Visit 2, subjects will start their respective trainings for 6 weeks. The one-on-one training sessions will be delivered via videoconferencing.

We will guide the subjects in the PD-MI group using personalized scripts during one-on-one mental imagery training 3 times a week for the first 4 weeks. We will also record the mental imagery scripts (each 5-10 min) for self-practice on none-training days in the first 4 weeks and for daily homework in the subsequent 2-week block. After each daily practice in the 2-week block, subjects will be asked to submit a detailed mental imagery diary via the Yale REDCap online survey platform. Subjects will also be called once a week in the 2-week block for check-in.

[figure not shown]
The control group (PD-Con) will receive psychoeducation 3 times a week for 4 weeks regarding cognitive functioning and brain health in PD. Subjects will receive private video links with pre-recorded PowerPoint lectures covering topics such as basic brain anatomy, neuroplasticity, attention-executive function, memory, speech-communication, hallucinations and delusions, sleep, diet, physical activity, mood disorders, stress, and social bonds. On no-lecture days and in the subsequent 2-week block, subjects will receive online quizzes covering the lecture topics to be completed via Yale REDCap online survey platform. Subjects will also be called once a week in the 2-week block for check-in.

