RBANS: Assesses 5 domains of cognition, 1) immediate memory, 2) Visuospatial/Constructional, 3) Language, 4) Attention, 5) Delayed Memory. Completion time is roughly 30 minutes.

Stroop test: Is a measure of attention that has the participant read through a list of words or naming colors as quickly as possible within 45 seconds.

F-A-S verbal fluency test: Measures verbal fluency by having the participant verbally produce as many words as possible that begin with the letters F, A, and S, within a one-minute timespan.

Trail Making Tests A & B: Consist of 25 circles spread over a sheet of paper, the subject is tasked with connecting each circle by following a specific pattern in a 5-minute timespan.

For all eligible subjects: We will administer the Neuro-QoL version 2 Cognitive Function survey to eligible subjects to assess self-reported cognitive functioning in everyday life.⁹⁷ We will administer the Modified Six-Elements Test.⁹⁸ The test consists of three tasks (simple arithmetic, written picture naming, dictation) each of which has two subtasks. The subject is required to attempt at least part of each of the six subtasks within 10 min, but without switching directly between subtasks within the same task category. The tests assess the ability to create and maintain goals and intentions, formulate a plan, organize behavior over time, and execute the plan at appropriate times.⁹⁹

For eligible subjects in the PD-MI group: We will perform a structured cognitive interview to determine the subject's cognitive difficulties during everyday tasks. Information gathered from this interview will help with personalized mental imagery guidance.

Visit 2: Baseline neuroimaging experiments: Visit 2 will be scheduled within two weeks following Visit 1. All subjects will complete the Questionnaire upon Mental Imagery (QMI) Vividness of Imagery Scale¹⁰⁰ for evaluation of baseline imagery skills. All subjects will then perform fMRI tasks in the scanner. The mental imagery tasks will always be performed before the video-watching tasks to avoid possible carryover effects from the videos.

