Online Homework and Quizzes: These will administered via the Yale REDCap online survey platform. Responses will be exported from REDCap.

- Quizzes on the psychoeducation material for the PD-Con group
- Surveys on the content of mental imagery homework for the PD-MI group

Clinical and Cognitive Evaluations:

- MDS-UPDRS and Hoehn & Yahr to assess disease severity (Visit 1)
- Wechsler Test of Adult Reading to determine premorbid IQ (Visit 1)
- RBANS test and executive function tests (Stroop, letter fluency (F-A-S), and Trail Making Test parts A and B) for a comprehensive cognitive evaluation (Visits 1, 3, and 4)
- Neuro-QoL survey (primary cognitive outcome) to assess the impact of cognitive functioning on activities of daily living (Visits 1, 3, and 4)
- Structured cognitive interview for the PD-MI group to determine subjects' cognitive difficulties during everyday tasks (Visit 1)
- QMI Vividness of Imagery Scale will serve as a manipulation check for the mental imagery intervention (Visits 2, 3, and 4)

- Modified Six-Elements Test as a performance-based measure of goal-directed planning and execution (Visits 1, 3, and 4)

Case report forms for each subject will be used to enter clinical evaluation results, and scores of paper-pencil tests, online surveys, and performance-based tests. All of this information will then be entered into a password-protected electronic database, which will be stored in a group-owned ([name] Lab) shared space on a Yale REDCap database.

Imaging Data:

Functional MRI data during mental imagery and video-watching tasks will be collected in a 3 Tesla human magnet at the MRRC (Visits 2, 3, and 4). The fMRI data will be used for functional connectivity analyses to evaluate the changes in whole-brain functional connectivity (primary imaging outcome) and other network measures as a result of the mental imagery intervention.

Imaging data will be transferred securely to workstations for analysis and stored on HIPAA-compliant secure central storage servers ("Storage@Yale") provided by the Yale IT Department for a monthly fee.

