5.4 Statistical Method

5.4.1 Statistical Design

This is a phase 1 randomized clinical trial aiming to enroll 120 subjects with Parkinson's disease (PD) assigned in parallel to the experimental PD-MI (N=60) and active control PD-Con (N=60) groups. The units of observation are the subjects in these groups. Subjects will be enrolled continuously and randomized to two groups using the "minimization" method.¹⁰¹ After truly randomly allocating the first 10 subjects, each subsequent subject will be allocated to either group considering the factors age, gender, and disease stage. This method will allow us to minimize the imbalance between the groups in terms of demographic and clinical characteristics while at the same time preserving the randomness of group allocation.

We will use independent-sample t-tests and nonparametric Mann-Whitney U tests to compare subjects characteristics between the PD-MI and PD-Con groups.

We will use mixed ANOVA tests with interaction terms to assess the short- and longer-term changes in cognitive and imaging outcomes before and after training.

Our overall statistical approach is designed to address the outcomes of four different aims:

AIM 1: To determine the effects of mental imagery training on goal-directed everyday cognitive functioning in PD

Primary outcome: Change in Neuro-QoL version 2 Cognitive Function scores.⁹⁷

Manipulation check: Change in QMI Vividness of Imagery Scale scores.¹⁰⁰

Neuro-QoL version 2 Cognitive Function scores (Visit 1) and QMI scores (Visit 2) obtained at baseline and immediately upon conclusion of the 6-week intervention (Visit 3) will be compared between the PD-MI and PD-Con groups using a 2x2 mixed ANOVA with an interaction term (dependent variables: test scores, between-subject factor: group, within-subject factor: time with two levels, i.e., baseline and post-training, interaction: group-by-time) ($p < 0.05$, two-tailed).

Secondary outcomes: Change in composite z-scores obtained from the executive function tests.

We will calculate a composite z-score from the executive function test scores (i.e., Stroop,⁹⁴ F-A-S letter fluency,⁹⁵ and Trail Making A-B tests⁹⁶) for all subjects.

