Composite executive function test z-scores obtained at baseline (Visit 1) and immediately upon conclusion of the 6-week intervention (Visit 3) will be compared between the PD-MI and PD-Con groups using a 2x2 mixed ANOVA with an interaction term (dependent variables: test scores, between-subject factor: group, within-subject factor: time with two levels, i.e., baseline and post-training, interaction: group-by-time) ($p < 0.05$, two-tailed).

Exploratory outcomes: 1) Change in RBANS scores,⁹³ 2) and change in The Modified Six-Element Test scores.⁹⁸

The RBANS and Modified Six-Element Test scores obtained at baseline (Visit 1) and immediately upon conclusion of the 6-week intervention (Visit 3) will be compared between the PD-MI and PD-Con groups using a 2x2 mixed ANOVA with an interaction term (dependent variables: test scores, between-subject factor: group, within-subject factor: time with two levels, i.e., baseline and post-training, interaction: group-by-time) ($p < 0.05$, two-tailed).

AIM 2: To determine the brain effects of mental imagery training in PD.

Primary outcome: Change in task-specific whole-brain pairwise functional connectivity.

We will generate group-level, task-specific, pairwise functional connectivity maps for the mental imagery and video-watching tasks using the CONN Toolbox.⁵³ These maps at baseline (Visit 2) and immediately upon conclusion of the 6-week intervention (Visit 3) will be compared between the PD-MI and PD-Con groups using a 2x2 mixed ANOVA with an interaction term (dependent variables: whole-brain pairwise functional connectivity maps, between-subject factor: group, within-subject factor: time with two levels, i.e., baseline and post-training,

interaction: group-by-time). We will use the false discovery rate (FDR)-correction for multiple comparisons ($p < 0.05$, two-tailed).¹⁰²

Secondary outcomes: Change in task-specific graph-based local and global network measures.

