Based on the pairwise functional connectivity maps, we will compute the clustering coefficient and betweenness centrality representing local and global graph measures, respectively, using the CONN Toolbox.⁵³ These graph measures associated with the mental imagery and video-watching tasks performed at baseline (Visit 2) and immediately upon conclusion of the 6-week intervention (Visit 3) will be compared between the PD-MI and PD-Con groups using a 2x2 mixed ANOVA with an interaction term (dependent variables: graph measures, between-subject factor: group, within-subject factor: time with two levels, i.e., baseline and post-training, interaction: group-by-time). We will use the FDR-correction for multiple comparisons ($p < 0.05$, two-tailed).¹⁰²

Behavioral scanning data: We will add up the number of key elements of the recorded mental imagery descriptions for each scan (e.g., entities, sensory descriptions, spatial/temporal references, thoughts, actions, emotions, task components) and average them across scans to obtain an average imagery content score per subject. We will also average the number of correct answers to content-related questions after video-watching scans to obtain an average accuracy score per subject. The average mental imagery content and video-watching accuracy scores performed at baseline (Visit 2) and immediately upon conclusion of the 6-week intervention (Visit 3) will be compared between the two groups using a 2x2 mixed ANOVA with an interaction term (dependent variables: average scores, between-subject factor: group, within-subject factor: time with two levels, i.e., baseline and post-training, interaction: group-by-time) ($p < 0.05$, two-tailed).

AIM 3: To determine whether the cognitive and brain effects of mental imagery training in PD are sustained

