5.4.6 Handling of Missing Data

We assume that the missing data will be missing at random. If the proportion of missing data is not more than 5%, we will ignore the missing data and perform complete case analyses. Otherwise, we will use multiple imputation to replace the missing data at follow-up for the primary cognitive outcome. Regardless of the proportion of missing data, we will constrain the voxelwise imaging analyses to complete cases because to our knowledge, there is no validated method to correct for missing data in such analyses.

6 Trial Administration

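### Subjects are randomised at Visit 1, but the connectivity, QMI, graph and in-scanner baselines are taken at Visit 2, after allocation and after a PD-MI-only interview

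*Combined protocol and SAP*

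**What the plan says.** **Allocation.** Section 4.1.1 says of Visit 1: "At the end of this visit, eligible subjects will be randomized to two groups, PD-MI and PD-Con". Section 5.1 also randomises at Visit 1, once the eligibility tests are scored. Visit 2 follows within two weeks.

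**Baselines.** Section 5.4.1 fixes the T0 visit for each measure:
- Aim 1: "Neuro-QoL version 2 Cognitive Function scores (Visit 1) and QMI scores (Visit 2) obtained at baseline".
- Aim 2, connectivity: "These maps at baseline (Visit 2) and immediately upon conclusion of the 6-week intervention (Visit 3) will be compared". The graph measures use the same two visits.
- Aim 2, behaviour in the scanner: "The average mental imagery content and video-watching accuracy scores performed at baseline (Visit 2").

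**Contact with PD-MI only.** Section 5.1, under Visit 1: "For eligible subjects in the PD-MI group: We will perform a structured cognitive interview". Section 5.1.1 gives the same visit for it ("cognitive difficulties during everyday tasks (Visit 1"), as does the visit list in Section 5.3.3. Section 4.1.1 instead has: "Subjects in the PD-MI group will be interviewed in Visit 2 to gather information about their daily activities and goals". It does not say whether that interview comes before or after the QMI and the scan.

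**Missing scans.** Section 5.4.6: "we will constrain the voxelwise imaging analyses to complete cases".

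The text says nothing about masking subjects or staff, or about withholding the allocation until the Visit 2 measures are finished.

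**The concern.** In a randomised trial, a baseline taken before allocation can differ between arms only by chance. That is what lets a group-by-time interaction be read as an effect of training. Here one primary outcome, the manipulation check and two further sets of measures have a T0 taken after allocation, when staff have already had to act on the arm in order to interview PD-MI subjects.

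Two measures are plainly open to this. QMI is a self-rating. The imagery-content score counts elements in the subject's own account of what was imagined. Either could move if a subject knows or guesses the arm, or has recently been interviewed about everyday tasks, which are also the subject matter of the scanner imagery. The same T0 enters the three-timepoint analyses of Aim 3, so a distortion would carry into the claim of sustained benefit.

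There is a second consequence, which does not depend on any shift. A subject who cannot complete the Visit 2 scan has already been randomised and becomes a loss from a complete-case imaging analysis, when that person could have been a screen failure.

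**Working it through.** The plan gives no figure on this point to reproduce. Its sample size (86 evaluable, 43 per arm, Section 5.4.2) is for Neuro-QoL and does not change. The check is of the order of events, followed by the algebra of a shifted baseline.

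**Order of events**

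| Event | Visit | Section |
|---|---|---|
| Neuro-QoL, executive tests, RBANS, Six-Elements baselines | 1 | 5.1, 5.4.1 |
| Randomisation | 1, at the end | 4.1.1 (also 5.1) |
| PD-MI structured interview | 1 | 5.1, 5.1.1, 5.3.3 |
| PD-MI interview on activities and goals | 2, order not stated | 4.1.1 |
| QMI baseline | 2 | 5.1, 5.4.1 |
| fMRI baseline: connectivity, graph measures, content and accuracy scores | 2 | 5.1, 5.4.1 |
| Arm-specific training instructions | 2, listed after QMI and fMRI | 5.3.3 |
| Start of training | after 2 | 4.1.1, 5.3.3 |

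Three things follow.

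1. Every measure with a Visit 2 baseline has a post-randomisation T0.
2. An interview restricted to PD-MI can only happen once the allocation is known. If it takes place at Visit 1, it precedes all the Visit 2 baselines.
3. On the explicit timing of Section 4.1.1, the Visit 1 measures precede allocation and lie outside this point. Section 5.1 mentions randomisation before it describes Neuro-QoL and the Six-Elements, but that is paragraph order only.

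**Effect of a shifted baseline**

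Let δ be the true training effect on the group-by-time contrast, s the shift in PD-MI at T0 that allocation or the interview causes, and p the fraction of s still present at T1.

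Contrast = (δ + p·s) − s = δ − (1 − p)·s, so bias = −(1 − p)·s.

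The values of s and p are assumptions; neither is in the documents. In SD units of the affected measure:

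| s | p = 0 | p = 0.5 | p = 1 |
|---|---|---|---|
| 0.1 | −0.10 | −0.05 | 0 |
| 0.2 | −0.20 | −0.10 | 0 |

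A negative s reverses the sign. A raised T0 in PD-MI hides benefit, and a lowered T0 creates the appearance of it.

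**What that could do to one test (illustration only)**

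Assume no training effect, p = 0, change-score SD of 1, 43 per arm and two-sided 5%. The standard error is √(2/43) = 0.216. A shift of 0.1 gives a noncentrality of 0.1/0.216 = 0.46 and a rejection rate of 7.4%. A shift of 0.2 gives 0.2/0.216 = 0.93 and 15%. These figures suit a single score such as QMI. They do not describe the FDR-corrected connectivity maps. Section 5.4.2 gives no planned effect for connectivity or QMI, so the bias cannot be stated as a share of one.

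**The case against.** The strongest reply is that randomised does not mean informed. The text never says that subjects learn their arm at Visit 1, and training instructions are listed after the QMI and the scan. Training itself starts after Visit 2. Both arms receive the same imagery instructions and practice before scanning, and the imagery goals are fixed across subjects. Section 4.1.1 puts a PD-MI interview at Visit 2, and the attachment list names only one structured interview, so the Visit 1 entry may be a misplacement. A mechanism is argued for QMI and imagery content but not for connectivity, graph measures or video accuracy. The size of any bias rests wholly on assumed values. Figures 3 and 4, which might show the order, were not available for this check.

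Much of this stands as a limit on the consequence. Reactivity is argued only for the two self-report-based measures, disclosure before the scan is a possibility and not a stated step, and the bias could be zero. None of it changes the sequence. Three sections place the PD-MI interview at Visit 1, and nothing in the text withholds the allocation from subjects or scanning staff.

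It is also said that a subject without a T0 scan cannot contribute to a complete-case change under either order, and that MRI screening by phone and the exclusion criteria make such failures uncommon. Both are fair, and there is no evidence of differential loss. The difference is that under the present order the failure is a loss after randomisation, and the 15% allowances in Section 5.4.2 are tied to the 6-week and 12-week periods, not to the interval between Visits 1 and 2.

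**Conclusion.** The point holds. Allocation precedes the T0 measurement of the primary imaging outcome, QMI, the graph measures and the in-scanner scores, and on Sections 5.1, 5.1.1 and 5.3.3 a PD-MI-only interview precedes it too. Confidence in the sequence is high. The size and direction of any bias are unknown: for an assumed shift of 0.1 to 0.2 SD, the absolute bias runs from 0 (the shift persists fully) to 0.10 to 0.20 SD (it vanishes by T1). The existing safeguards narrow the exposure but do not restore a pre-allocation baseline. Neuro-QoL, the executive composite, RBANS and the Six-Elements are unaffected on the Section 4.1.1 timing. This is an avoidable weakness that should be corrected; it does not undermine the primary cognitive comparison.

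**What to change.** 1. Randomise at the end of Visit 2, after the QMI and both fMRI tasks. Hold every PD-MI interview and the arm-specific training instructions after that point.
2. If allocation must stay at Visit 1, do not disclose it to subjects or scanning staff, and hold no PD-MI interview, until the Visit 2 QMI and scan are complete.
3. Reconcile Section 4.1.1 with Sections 5.1, 5.1.1 and 5.3.3 on whether there are one or two interviews and when each takes place.
4. State in Section 5.1 that Neuro-QoL and the Six-Elements are given before allocation.
5. If neither 1 nor 2 is adopted, say in the analysis plan and in reports that these baselines are post-randomisation.

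The cost is protocol wording and a reordered visit. The minimisation factors (age, gender, disease stage) are known by Visit 1, so later allocation loses nothing there. Visit 2, budgeted at 2 hours, becomes longer for PD-MI. Because Section 5.3.3 starts training immediately after Visit 2, preparing personalised scripts may need a short gap, which should be the same in both arms. Option 2 keeps the present allocation point but still moves any Visit 1 interview.

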4.1.2 Study Date Range and Duration

The expected length of the study is 6 years. See Table 1 below for the study timeline.

Table 1. Study Timeline

Year 1	Data collection and analysis for primary objectives. Start data analysis for secondary objectives.
Year 2	Data collection and analysis for primary and secondary objectives.
Year 3	Wrap up data analysis of primary objectives. Start writing manuscripts.
Year 4	Complete data collection. Wrap up data analysis for secondary objectives. Continue writing manuscripts.
Years 5-6	Complete all statistical analyses. Present and publish findings. Propose mental imagery training manual. Refine the study procedures and start implementing the phase 2 trial.

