5.4.5 Interim Analysis

N/A

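### Table 1 closes the primary-objective analysis in Year 3 but ends data collection in Year 4, and nothing ties the between-arm test to a data lock or masks earlier work

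*Combined protocol and SAP*

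**What the plan says.** Table 1 in section 4.1.2 sets out the calendar. Its opening row reads "Data collection and analysis for primary objectives. Start data analysis for secondary objectives", so analysis begins in the same year as collection. The row after that continues both activities. The third row, "Wrap up data analysis of primary objectives. Start writing manuscripts", brings the work on the primary objectives to a close. Collection itself is brought to an end one row later, where the fourth-year entry is "Complete data collection. Wrap up data analysis for secondary objectives" and writing carries on. The final row, covering the last two years, is where the table places completion of every statistical analysis, presentation and publication.

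The section headed "5.4.5 Interim Analysis" contains only N/A.

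Section 5.4.1 says "Subjects will be enrolled continuously and randomized to two groups", so data accumulate over the recruitment period. Under Aim 1 the primary cognitive scores "will be compared between the PD-MI and PD-Con groups using a 2x2 mixed ANOVA with an interaction term", with "interaction: group-by-time) ($p < 0.05$, two-tailed" as the criterion. Aim 2 uses the same between-arm design for connectivity, with false discovery rate control across connections. Aim 3 extends it to three time points.

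Section 4.1.1 places Visit 4 (T2) twelve weeks after Visit 3 (T1). The Synopsis makes the effect of six weeks of training the primary objective. The Synopsis and section 3.3 make the sustained 12-week effect the secondary objective. Section 4.2.1 nevertheless lists change at both T1 and T2 under the primary outcomes.

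Section 6.3 gives the principal investigator and research staff access to the data for analysis. Section 6.10 has an internal team monitor the study without a DSMB. The documents describe no data lock and no masking of assessors or analysts.

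**The concern.** The only inferential analysis specified for the primary outcomes is a comparison of the two arms. A calendar that analyses the primary objectives during continuous enrolment, and closes that analysis before collection ends, sits badly with a statement that interim analysis does not apply.

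Two things are at stake. First, following the table literally could close the primary analysis on an incomplete T1 data set. Second, arm-level results could become known to people still running visits. The primary cognitive outcome is self-reported, the imagery training is personalised and one-on-one, and there is no independent monitoring. Knowledge of an emerging difference could therefore affect expectations or the choice of when to report, even if nobody stops the trial early.

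**Working it through.** **1. What the sample size budgets for.** Section 5.4.2 uses f = 0.266, two measurements, alpha 0.05 and power 0.80, and obtains 86. The between-factor formula is λ = f²·N·m / (1 + (m−1)ρ), tested on F with 1 and N−2 degrees of freedom. The plan gives no correlation ρ; 0.5 is assumed here.

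- λ = 0.266² × 86 × 2 / 1.5 = 8.11, giving power 0.804. The figure of 86 is reproduced. With ρ = 0.3 or 0.7 the same formula needs 76 or 98.
- Dropout: 86/0.85 = 101.2 and 101/0.85 = 118.8, in line with the stated 120.

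This allows for one test at 0.05. It contains no allowance for repeated looks.

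**2. Can all T1 data be in hand when the primary analysis closes?** Let collection end w weeks into Year 4 with a Visit 4. That subject's Visit 3 was at week w − 12 of Year 4. Take the wrap-up as late as possible, on the last day of Year 3.

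- w ≤ 12: that T1 visit falls in Year 3, so a complete T1 analysis in Year 3 is possible.
- w = 26: it falls in week 14 of Year 4, after the wrap-up.
- w = 52: it falls in week 40 of Year 4.

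The documents do not give w. As an illustration only, suppose T1 visits are spread evenly from the start of Year 1. The share arriving after Year 3 is then (w − 12) / (156 + w − 12). That is 0 at w = 12, 14/170 = 8% at w = 26 and 40/196 = 20% at w = 52. An earlier wrap-up within Year 3 leaves out more.

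**3. What unadjusted looks would do.** Under the null hypothesis, let Z(t) = B(t)/√t, where B is Brownian motion and t is the fraction of information. Count a false positive if |Z| > 1.96 at any look. Two million simulated paths, checked by direct multivariate normal integration, give:

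| Assumed looks (information fraction) | Type I error, simulated | Integrated |
|---|---|---|
| One, at the end | 0.050 (by design) | 0.050 |
| 0.90, 1 | 0.0650 | 0.0648 |
| 0.75, 1 | 0.0735 | 0.0734 |
| 0.50, 1 | 0.0832 | 0.0831 |
| 1/3, 2/3, 1 | 0.1072 | 0.1073 |
| 0.25, 0.50, 0.75, 1 | 0.1262 | 0.1262 |

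The number and timing of looks are assumptions, because the documents specify none. The figures also assume that the first significant result is the one reported.

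**The case against.** The strongest reply is that Table 1 is only loosely worded. Section 5.4.3 uses the word analysis for composite scoring, for counting imagery elements and for fMRI preprocessing, and then says that the resulting scores go into statistical analyses. Table 1 itself reserves completion of the statistical analyses, and publication, for Years 5-6. On that reading, Years 1-3 are scoring and image processing, and the arms are compared later. This stands in part. A reader might infer that the protocol schedules between-arm tests from Year 1, but the documents do not say so. They also do not say the opposite.

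A second reply is that the primary objective is the six-week effect, so Year 4 collection may consist only of remaining T2 visits. A reader might infer from section 4.2.1 that the primary analysis cannot be finished in Year 3 because T2 change is listed as primary. That goes too far, since the Synopsis and section 3.3 assign the 12-week effect to the secondary objective and section 5.4.1 analyses it separately as Aim 3. The reply fully rescues Table 1 only if collection stops within about the first 12 weeks of Year 4.

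A third reply is that no looks, stopping rule or adaptation are planned. That is correct. A reader might infer that the trial's type I error is 8% to 13%, but that requires looks and a reporting rule that the documents do not contain. Unused early looks leave a single final test at 0.05.

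Finally, the documents do not say that the same individuals train, test and analyse. They give research staff data access and describe no masking, which leaves the possibility open. The control lectures are pre-recorded, so staff have little scope to influence that arm's delivery beyond check-in calls.

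**Conclusion.** The concern holds in a limited form. Table 1 and section 5.4.5 need reconciling: the primary-objective analysis closes a calendar year before collection is completed, and no section defers the arm comparison to a lock or masks earlier work. Unless collection ends within about 12 weeks of the start of Year 4, some T1 data arrive after that analysis has closed. Arm comparison on accumulating data is allowed by the wording; it is not a stated plan.

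Any inflation is conditional. It would be about 6.5% or 7.3% with one early look at 90% or 75% of the data plus a final look, and 8.3% to 12.6% with two to four equally spaced looks, if the first significant result were reported. It is nil if early results are not acted on. Exposure of unmasked staff to arm results is a separate risk that cannot be quantified from the documents. This is a cheap improvement; it does not show the design to be invalid.

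**What to change.** Replace the N/A in section 5.4.5 with a statement that:

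- no outcome is compared by arm until the last T1 visit of all randomised subjects is complete and the T1 data are locked;
- work before that point is limited to scoring, preprocessing and quality control without arm labels;
- any T1 arm results are withheld from staff conducting visits, and are not published, until the last T2 visit is complete.

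Amend Table 1 so that the primary-objective analysis and manuscripts follow the T1 lock, and the sustained-effect analysis follows the T2 lock. If early looks are in fact intended, section 5.4.5 should instead declare their timing, the alpha control and who sees the results.

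The cost is a few sentences and a few table cells, plus keeping arm labels and T1 results away from visit staff. The sample size and study procedures do not change. The downside is that first results appear later.
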